Given the hypothesis generating nature of this study, the Sponsor may conduct up to two interim analyses of efficacy. The decision to conduct such an interim analysis and its timing will be documented in the Sponsor's study master file prior to the conduct of the interim analysis. The Clinical Study Report will also document that such an interim analysis occurred. The interim analysis, should it occur, will be performed and interpreted by members of the Sponsor study team and management who would then be unblinded to treatment group (MTAU9937A or placebo).

LIST OF ABBREVIATIONS AND DEFINITIONS OF TERMS

Abbreviation	Definition
[¹⁸ F]GTP1	fluorine-18 Genentech tau probe 1
A β	β -amyloid
AD	Alzheimer's disease
ADA	anti-drug antibody, also known as anti-therapeutic antibody (ATA)
ADAS-Cog11	Alzheimer's Disease Assessment Scale—Cognitive Subscale, 11-item version
ADCS-ADL	Alzheimer's Disease Cooperative Study—Activities of Daily Living Inventory
ADL	activities of daily living
CaGI-Alz	Caregiver Global Impression Scales for Alzheimer's disease
CDR	Clinical Dementia Rating
CDR-GS	Clinical Dementia Rating—Global Score
CDR-SB	Clinical Dementia Rating—Sum of Boxes
C _{max}	maximum concentration
COA	clinical outcome assessment
CRO	contract research organization
CSF	cerebrospinal fluid
C-SSRS	Columbia-Suicide Severity Rating Scale
DVF	Diagnostic Verification Form
EC	Ethics Committee
eCRF	electronic Case Report Form
EDC	electronic data capture
Fc	fragment crystallizable
FcRn	neonatal Fc receptor
FDA	Food and Drug Administration
GLP	Good Laboratory Practice
GTP1	Genentech tau probe 1
HbA _{1c}	hemoglobin A _{1c}
HBsAg	hepatitis B surface antigen
HCV	hepatitis C virus
HIPAA	Health Insurance Portability and Accountability Act
HV	healthy volunteer
ICH	International Council for Harmonisation
IMC	Internal Monitoring Committee
IMP	investigational medicinal product

Abbreviation	Definition
IND	Investigational New Drug (Application)
IRB	Institutional Review Board
IxRS	interactive voice or web-based response system
LP	lumbar puncture
MMSE	Mini-Mental State Examination
MRI	magnetic resonance imaging
NIA-AA	National Institute on Aging–Alzheimer’s Association
NPI	Neuropsychiatric Inventory
OLE	open-label extension
PD	pharmacodynamic
PET	positron emission tomography
PK	pharmacokinetic
Q2W	every 2 weeks
Q4W	every 4 weeks
QTcF	QT interval corrected through use of Fridericia’s formula
QW	once a week
RBR	Research Biosample Repository
SNP	single nucleotide polymorphism
T4	thyroxine
TK	toxicokinetic
ULN	upper limit of normal
WES	whole exome sequencing
WGS	whole genome sequencing
YTE	combination of M249Y, S251T, and T253E mutations in the heavy chain component of an antibody Fc region

1. **BACKGROUND**

1.1 **BACKGROUND ON ALZHEIMER'S DISEASE**

Alzheimer's disease (AD) is the most common cause of dementia, affecting an estimated 5.7 million individuals in the United States (Alzheimer's Association 2018). Worldwide, it is estimated that 46.8 million people have AD or other dementias (Prince et al. 2015).

The disease is characterized pathologically by the accumulation in the brain neocortex of extracellular β -amyloid ($A\beta$) peptide-containing plaques and intracellular neurofibrillary tangles containing aggregates of the microtubule associated protein tau. Diagnosis is made through the clinical assessment of the neurologic and neuropsychiatric signs and symptoms of AD and the exclusion of other causes of cognitive dysfunction. AD is commonly classified into preclinical, prodromal, mild, moderate, and severe stages by the presence and severity of clinically relevant functional and/or cognitive decline, and categorization is often facilitated by global measures, such as the Clinical Dementia Rating (CDR) scale (Morris 1993) or the Mini-Mental State Examination (MMSE; Folstein et al. 1975). Approved medical therapies that inhibit acetylcholinesterase activity or antagonize *N*-methyl-D-aspartate receptors in the brain may temporarily improve the symptoms of AD in some patients but do not modify the progression of the disease (Cummings 2004).

The deposition of extracellular amyloid plaques and intracellular tau aggregates in the brain are the hallmark pathologic findings in AD, first reported by Alois Alzheimer in 1906. Intracellular neurofibrillary tangles are composed of aggregated and abnormally phosphorylated tau protein. Tau, encoded by the *MAPT* gene, is expressed in the human brain as six splice isoforms, with lengths of 352–441 amino acids. The six isoforms comprise combinations of three variant near-amino-terminal repeat domains (0N, 1N, and 2N) and two variant carboxy-terminal repeat domains (3R and 4R) (Wang and Mandelkow 2016). While the intracellular aggregates are found as neurofibrillary tangles in the neuronal soma and as neuropil threads in the dendritic compartment, it is believed that the spread of tau pathology through the brain is mediated by soluble tau in the extracellular brain environment (Braak and Tredici 2015; Wang and Mandelkow 2016).

The spatial distribution of tau pathology in patients with AD correlates with decline in the cognitive domains subserved by the affected cortical networks (Ossenkoppele et al. 2016). Knockout of the tau gene in an AD transgenic mouse model is protective against cognitive deficits (Roberson et al. 2007). Therapies that reduce the spread of tau in the brain may alleviate cognitive dysfunction and block further synaptic loss, axon degeneration, and neuronal cell death.

Targeting the spread of tau in the moderate stages of AD may prove to be more efficacious than prior interventions that have targeted $A\beta$ in this stage of the disease and failed to ameliorate further clinical decline (Doody et al. 2013, 2014; Salloway et al. 2014; Egan et al. 2018). Whereas most of the accumulation of $A\beta$ pathology may have

already occurred by the time patients with AD reach the moderate stages of disease, tau pathology appears to continue to increase (Jack et al. 2013). Studies that examine tau indices via neuropathology (Nelson et al. 2012), cerebrospinal fluid (CSF) tau levels (Kanai et al. 1998) and tau positron emission tomography (PET) imaging (Ishiki et al. 2015) have each suggested continued progression of tau pathology in patients with AD of at least moderate severity.

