Patients will be randomly assigned to receive MTAU9937A (4500 mg) or placebo administered by IV infusion in a 1:1 ratio. All patients participating in the OLE will receive MTAU9937A 4500 mg IV infusion. Because both *APOE* genotype and baseline cognitive performance may be associated with subsequent rates of clinical progression, randomization will be stratified by both *APOE* status (*ApoE4*+ vs. *ApoE4*-) and screening MMSE scores (16–18 vs. 19–21).

Patients will be selected on the basis of clinical diagnosis of probable AD dementia. Clinical diagnosis for each patient must be supported by information provided on a Diagnostic Verification Form (DVF), which must be reviewed and approved by the Sponsor or Sponsor delegate.

Eligible patients must be 50–85 years old at the beginning of screening, meet diagnostic criteria for probable AD dementia, and have evidence of cerebral amyloidosis as indicated by CSF analysis (i.e., CSF-enrolled patients) or positive amyloid PET scan by qualitative read (i.e., PET-enrolled patients). The choice between CSF versus PET for determination of cerebral amyloidosis should be made on the basis of the capability of an individual site and/or the preference of an individual patient. If a patient is amyloid negative based on one of the two modalities (CSF assessment or amyloid PET), then the patient may undergo assessment with the other modality during screening; amyloid positivity by either modality is sufficient for eligibility.

At the time of screening, patients must have a MMSE score between 16 and 21 (inclusive) and a Clinical Dementia Rating–Global Score (CDR-GS) of 1 or 2. Patients will be eligible for the study regardless of whether they are receiving standard-of-care symptomatic medications for AD (e.g., cholinesterase inhibitors, memantine, and/or the medical food supplement Souvenaid®). These medications must have been stable for ≥ 2 months prior to screening, and there should be no a priori planned initiation, discontinuation, or dose changes for these medications during the study (double-blind treatment and OLE treatment periods). However, following the initiation of study drug, standard-of-care symptomatic medications for AD may be initiated, dose adjusted, or discontinued as deemed clinically appropriate.

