The entire study, from screening of the first patient to the end of the study, is expected to last up to 60 months.

Investigational Medicinal Products

Test Product (Investigational Drug)

MTAU9937A is the investigational medicinal product (IMP) in this study. Depending on local classification, the [¹⁸F]GTP1 tau PET radioligand and/or the amyloid PET radioligand(s) may be considered non-investigational medicinal products or IMPs.

Study drug (MTAU9937A or placebo) will be administered intravenously in the double-blind treatment period, and MTAU9937A will be administered intravenously in the optional OLE period. Study drug administration will occur Q2W for the first three doses of the double-blind treatment period and Q4W thereafter during the double-blind treatment period. MTAU9937A will be administered Q4W in the OLE period.

Non-Investigational Medicinal Products

Depending on local classification, the [¹⁸F]GTP1 tau PET radioligand and/or the amyloid PET radioligand(s) may be considered non-investigational medicinal products or IMPs.

Statistical Methods

Primary Analysis

The co-primary efficacy endpoints are change in ADAS-Cog11 and ADCS-ADL scores from baseline to the last visit of the double-blind treatment period (Week 49 for Cohort 1 or Week 61 for Cohort 2). The difference in mean change from baseline to the last visit of the double-blind treatment period between MTAU9937A- and placebo-treated patients will be estimated using an analysis of covariance model adjusting for *ApoE4* status (*ApoE4+* vs. *ApoE4-*), screening MMSE (16–18 vs. 19–21), baseline [¹⁸F]GTP1 PET standard uptake value ratio, age, and baseline ADAS-Cog11 or ADCS-ADL scores, and if appropriate, the number of missed study drug infusions during the double-blind treatment period due to the COVID-19 pandemic. Confidence intervals, as well as least squares estimates, will be used to aid in interpretation of study results.

Determination of Sample Size

This study will enroll approximately 260 patients randomized to either an IV active dose arm or to an IV placebo dose arm in a 1:1 ratio. This sample size provides approximately 80% power to detect a 35% relative reduction in mean ADAS-Cog11 change from baseline when MTAU9937A is compared with placebo assuming an average decline of 6 points for placebo-treated patients, a standard deviation across patients of 7.5, a 10% dropout rate, and a two-sided $\alpha=0.2$ significance level.

Interim Analyses

Optional Interim Analysis

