4.4 CONCOMITANT THERAPY

Concomitant therapy consists of any medication (e.g., prescription drugs, over-the-counter drugs, vaccines, herbal or homeopathic remedies, nutritional supplements) used by a patient in addition to protocol-mandated treatment from 3 months prior to screening until the final study visit. However, any agent that targets A β used by the patient at any time during their life is also considered to be a concomitant therapy. All such medications should be reported to the investigator and recorded on the appropriate Concomitant Medications eCRF.

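### Baseline symptomatic AD drug use is recorded for every patient but is not a covariate in the ANCOVAs, which forgoes a small gain in precision without biasing the comparison

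*Combined protocol and SAP*

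**What the plan says.** **Entry.** The synopsis and Section 3.1.1 admit both users and non-users: "Patients will be eligible for the study regardless of whether they are receiving standard-of-care symptomatic medications for AD". Cholinesterase inhibitors, memantine and the medical food Souvenaid are given as examples. For users, "These medications must have been stable for ≥ 2 months prior to screening", and no change may be planned at entry.

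**After the first dose.** The same passages, the inclusion criteria and Section 4.4.1 allow changes: "However, following the initiation of study drug, standard-of-care symptomatic medications for AD may be initiated, dose adjusted, or discontinued as deemed clinically appropriate".

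**Expected effect.** Section 1.1 says the approved drugs "may temporarily improve the symptoms of AD in some patients" but do not alter progression. No size is given on either co-primary scale.

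**Recording.** Section 4.4 covers medicines and nutritional supplements from 3 months before screening to the last visit: "All such medications should be reported to the investigator and recorded on the appropriate Concomitant Medications eCRF". Section 4.5.2 and the schedules of activities agree.

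**Analysis.** The synopsis and Section 6.4.1 say the difference in mean change "will be estimated using an analysis of covariance model adjusting for" ApoE4 status, screening MMSE category, baseline tau PET uptake ratio, age, the baseline score and, if appropriate, COVID-related missed infusions. Section 6.4.2 analyses the secondary endpoints in the same way. Symptomatic drug use is not in the list, and it is not among the examples of baseline summaries in Section 6.3.

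**The concern.** Whether a patient is already on a symptomatic drug at entry could plausibly predict change over 49 or 61 weeks. A patient who enters untreated can still gain a temporary improvement by starting such a drug, and one already on treatment may have less room to do so. The documents do not show that this happens, but they give enough reason to expect some association, and the variable is already collected before the first dose.

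A baseline predictor left out of an ANCOVA has two consequences. Its share of the outcome variance stays in the residual, which widens the confidence interval. Any chance difference between arms in the proportion of users also passes into the estimate unadjusted. The planned effect is only 2.1 ADAS-Cog11 points against a standard deviation of 7.5, so a cheap gain in precision is worth considering.

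**Working it through.** **Inputs from Section 6.1:** 260 patients, 1:1 (130 per arm); placebo decline 6 points; 35% relative reduction; SD 7.5; 10% dropout; two-sided alpha 0.2.

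**Assumed, because the documents give no figures:** proportion of baseline users p = 0.3 to 0.7; difference d in mean ADAS-Cog11 change between users and non-users = 1 to 3 points.

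**Step 1: the plan's own figure.**
- Target difference = 0.35 × 6 = 2.1 points. Evaluable per arm = 130 × 0.9 = 117.
- SE = 7.5 × √(2/117) = 0.981, and 2.1/0.981 = 2.142.
- The critical value for two-sided alpha 0.2 is 1.2816.
- Power, both tails counted = Φ(2.142 − 1.2816) + Φ(−2.142 − 1.2816) = 0.8051 + 0.0003 = 80.5%. The stated figure of about 80% is reproduced.

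**Step 2: precision gained from the covariate.** The share of variance explained is R² = p(1−p)d²/7.5². The residual SD becomes 7.5 × √(1 − R²), and power is recomputed as in Step 1.

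| p | d | R² | Power |
|---|---|---|---|
| 0.3 or 0.7 | 1 | 0.4% | 80.7% |
| 0.3 or 0.7 | 2 | 1.5% | 81.0% |
| 0.3 or 0.7 | 3 | 3.4% | 81.5% |
| 0.5 | 1 | 0.4% | 80.7% |
| 0.5 | 2 | 1.8% | 81.1% |
| 0.5 | 3 | 4.0% | 81.7% |

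This treats 7.5 as the residual SD of the planned model and treats drug use as unrelated to the covariates already in it. If drug use is correlated with baseline score or MMSE category, the gain is smaller.

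**Step 3: chance imbalance.**
- The SD of the between-arm difference in the proportion of users is √(2p(1−p)/117) = 0.060 (p = 0.3 or 0.7) to 0.065 (p = 0.5).
- An imbalance of at least 10 percentage points, in either direction, has probability 9.5% to 12.6%.
- Such an imbalance of exactly 10 points moves the unadjusted estimate by 0.10 × d = 0.1 to 0.3 points, or 5% to 14% of 2.1.
- The 95% range of the shift is 1.96 × 0.060 × 1 = 0.12 points to 1.96 × 0.065 × 3 = 0.38 points either way, against an SE of 0.98. Its mean is zero.

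**Step 4: cost.** One degree of freedom. With a noncentral t calculation, going from 232 to 231 error degrees of freedom lowers power by less than 0.001 percentage point if the covariate explains nothing.

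No matching calculation is possible for ADCS-ADL, because the documents give no SD or effect for it.

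**The case against.** The strongest reply is that nothing in the primary analysis is wrong. Allocation is randomised 1:1 and blinded (Section 4.2), users must be on a stable regimen at entry, and baseline score and MMSE category are already in the model. Chance imbalance has mean zero and lies within the test's error rate. The gain is at most about 1 percentage point of power, on assumed inputs. All of this stands, and it confines the point to efficiency.

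Three stronger readings are tempting and are not supported.

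- **That omitting drug use biases the result or leaves it uncontrolled.** Randomisation balances baseline use in expectation. Section 1.1 reports a temporary benefit in some patients, not an effect on ADAS-Cog11 or ADCS-ADL.
- **That drug use should have been a stratification factor.** Strata are APOE status and screening MMSE. Adding a covariate captures the modest gain available, and the documents give no reason to require a third factor.
- **That changes after the first dose distort the treatment effect.** This would need starts to differ by arm. The documents give no start rates, no between-arm difference and no effect in points, so any figure would be a product of assumptions. Section 6 groups patients as randomised. Keeping all ratings under that grouping is a sound treatment-policy comparison, even though the strategy is not named. These changes follow randomisation and may respond to treatment, so adjusting for them could itself introduce bias.

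Two limits also apply. Section 6.5, on safety, refers to a Data Analysis Plan that is not in the material, so a covariate or tabulation specified there cannot be ruled out. The rationale for Version 5 reports that no treatment effect was seen on tau PET in the double-blind period, which suggests that between-arm results have already been examined. A new covariate in the primary model could then be post hoc.

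**Conclusion.** The point holds as one of efficiency. A baseline variable that the protocol gives reason to think prognostic is collected for every patient and left out of the ANCOVAs. The omission costs a little precision and leaves chance imbalance in that variable unadjusted. With 30–70% users and a 1–3 point difference in mean change, both assumed, power would rise from 80.5% to about 80.7–81.7%. The comparison as planned remains valid, and no conclusion about bias, stratification or the effect of later drug changes follows.

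**What to change.** Add baseline symptomatic AD medication, none versus any, as a covariate in the ADAS-Cog11 and ADCS-ADL ANCOVAs and in the CDR-SB and MMSE models. Derive it from Concomitant Medications eCRF records dated before the first dose, and state whether Souvenaid counts as use, since the protocol names it alongside cholinesterase inhibitors and memantine. If the double-blind data have been unblinded, leave the planned model as primary and report this one as a declared sensitivity analysis.

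Leave the permission to change symptomatic drugs as it is, and keep all later ratings in the as-randomised primary analysis. By-arm counts of starts, dose changes and stops would be useful optional supportive reporting, but they should not enter the model.

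The cost is one line of analysis text per model and 1 degree of freedom. No new data are needed.

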1.2 BACKGROUND ON MTAU9937A

1.2.1 Nonclinical Information

MTAU9937A is a pan-tau IgG4 monoclonal antibody that has potential to treat tauopathies (including AD and primary tauopathies). MTAU9937A is designed to bind and intercept all extracellular tau isoforms, in order to stop or slow cell-to-cell spread and propagation of tau toxicity and pathology throughout cortical and sub-cortical networks. The IgG4 backbone was chosen for MTAU9937A because it has reduced Fc_Y receptor binding affinity compared with the human IgG1 subclass, and thus a reduced immune effector response. MTAU9937A has demonstrated protection of neurons in the presence of microglia, in response to exposure to toxic species of tau in cell-based experiments (see the MTAU9937A Investigator's Brochure for details). MTAU9937A has also been engineered to contain three mutations (M249Y, S251T, and T253E [YTE]) in the heavy chain component of the fragment crystallizable (Fc) region of the antibody that enhance binding to the neonatal Fc receptor (FcRn) and have been shown to slow peripheral antibody clearance in humans, potentially augmenting exposure levels (Robbie et al. 2013).

A murine surrogate of MTAU9937A showed dose-dependent reduction in accumulation of tau pathology in a transgenic model (hTau P301L.Tg) overexpressing human tau. In addition, MTAU9937A prevented toxic tau species from entering cultured neurons and protected these neurons from tau-mediated toxicity and death.

There were no MTAU9937A-related adverse findings in the Good Laboratory Practice (GLP) 5-week, repeat-dose toxicity study in which cynomolgus monkeys were administered MTAU9937A at doses up to 300 mg/kg/week IV. MTAU9937A-related clinical pathology findings were limited to increases in neutrophils, fibrinogen, globulin (possibly because of the presence of high levels of test article), and/or decreases in albumin, suggestive of a mild inflammatory response, as well as mild transient decreases in glucose and mild decreases in platelets. The findings were not considered adverse as they were mild, transient, or both, and no anatomic findings explained or correlated with the findings. On the basis of this 5-week toxicity study in monkeys, the no-observed-adverse-event level was determined to be the highest dose tested, 300 mg/kg/week (mean area under the concentration–time curve from toxicokinetic [TK] Day 0 to TK Day 30 of 184,000 $\mu\text{g} \cdot \text{day}/\text{mL}$ and a maximum concentration [C_{\max} ; post-first dose] of 7,280 $\mu\text{g}/\text{mL}$).

In addition, MTAU9937A was also locally well tolerated following single SC injection in rabbits.

In support of chronic administration of MTAU9937A in patients, a GLP 26-week, repeat-dose, toxicity study has been conducted in cynomolgus monkeys and is currently in the reporting phase. Preliminary in-life data show that MTAU9937A was well tolerated by cynomolgus monkeys following 27 weekly, IV doses up to 300 mg/kg with no MTAU9937A-related adverse effects noted (refer to the MTAU9937A Investigator's Brochure for additional details regarding results of this study).

Refer to the MTAU9937A Investigator's Brochure for further details regarding the nonclinical studies.

1.2.2 Clinical Information

The experience with MTAU9937A in humans consists of data from one completed Phase I study (GN39058), *one completed* Phase II study (GN39763), and this ongoing Phase II study (GN40040).

Study GN39058 (clinicaltrials.gov identifier NCT02820896) was a randomized, placebo-controlled, double-blind, ongoing Phase I study that assessed the safety, tolerability, and pharmacokinetics of IV and SC MTAU9937A in 65 healthy volunteers (HVs) and 10 patients with mild to moderate AD. It consisted of a single-ascending dose part (six IV cohorts, with doses from 225 mg to 16,800 mg, and one SC cohort at 1200 mg) and a multiple-dose part (two IV cohorts each receiving 8400 mg IV once a week [QW] \times 4 weeks). All single-dose cohorts consisted of only HVs; one multiple-dose cohort consisted of HVs and the other multiple-dose cohort consisted of patients with AD. The initial single-dose IV cohort consisted of 3 HVs, randomized to a 2:1 ratio (MTAU9937A:placebo). The remainder of the single-dose IV cohorts consisted of 8 HVs, randomized to a 6:2 ratio (MTAU9937A:placebo). The single-dose SC cohort consisted of 12 HVs, all treated with MTAU9937A. Each of the two multiple-dose IV cohorts consisted of 10 subjects, randomized to an 8:2 ratio (MTAU9937A:placebo). A total of 44 HVs received single doses of MTAU9937A with a range of 225–16,800 mg IV or SC (32 HVs received IV doses, 12 HVs received SC doses), and 16 participants (8 HVs and 8 patients with mild to moderate AD) each received doses of 8400 mg IV QW \times 4 (except for 1 HV, who was mistakenly administered a first dose of 4200 mg, followed by three doses of 8400 mg).

Study GN39763 was a global randomized, double-blind, placebo-controlled, parallel-group Phase II study investigating the safety and efficacy of MTAU9937A (at doses of 1500 mg, 4500 mg, or 8100 mg) in patients with prodromal to mild AD. Of the 457 patients who were randomized into treatment arms, 441 received at least one dose of MTAU9937A or placebo in the blinded portion of the study, 369 completed the blinded portion of the study, and 360 received at least one dose of MTAU9937A in the OLE portion of the study. The study was discontinued on 23 September 2020, after

top-line analyses of data from the 73-week double-blind, placebo-controlled portion of the study indicated similar rates of progression on the primary efficacy endpoint (Clinical Dementia Rating Sum of Boxes) in the placebo arm and all three MTAU9937A arms. Similar rates of progression on the secondary efficacy cognitive endpoints (Repeatable Battery for the Assessment of Neuropsychological Status Total Index and the 13-item version of the Alzheimer's Disease Assessment Scale—Cognitive Subscale) and secondary efficacy functional endpoints (Alzheimer's Disease Cooperative Study—Activities of Daily Living and Amsterdam Instrumental Activities of Daily Living Questionnaire) were seen in the placebo arm and all three MTAU9937A arms over the 73-week treatment period. Furthermore, on the exploratory endpoint of brain tau burden as measured by fluorine-18 Genentech tau probe 1 ($[^{18}\text{F}]\text{GTP1}$) tau PET imaging, similar rates of overall cortical tau accumulation were seen in the placebo arm and all three MTAU9937A arms over the 73-week treatment period.

MTAU9937A has been generally well tolerated in HVs and patients with AD (please refer to the MTAU9937A Investigator's Brochure for further details). No adverse drug reactions have been identified with MTAU9937A. Potential risks associated with MTAU9937A are discussed in Section 5.1.1.

The pharmacokinetics of MTAU9937A were evaluated in Study GN39058 following single (225–16,800 mg), weekly (8400 mg \times 4 doses) IV, or single (1200 mg) SC administration to HVs and to patients with mild to moderate AD. Upon IV administration, MTAU9937A exhibited biphasic disposition, and the plasma half-life had a range of 22.8–45.7 days. The mean SC bioavailability estimated from the SC cohort (1200 mg) was approximately 69%. Upon weekly IV administration, the pharmacokinetics of MTAU9937A were comparable between HVs and patients with AD. Dose proportionality assessment demonstrated that serum pharmacokinetics increased proportionally with dose following single-dose IV administration. MTAU9937A was detected in the CSF, suggesting penetration into the CNS. *Pharmacokinetic results from the Phase II study (GN39763) in patients with prodromal to mild AD are consistent with PK data from HVs and patients with AD in the Phase I study (GN39058).*

Refer to the MTAU9937A Investigator's Brochure for further details on clinical studies.

